# Primary end-point:

• Percentage of patients with treatment failure at day 7 after randomisation. Treatment failure is defined as either failure to administer allocated treatment for any reason or the presence of diarrhoea on day 7 after randomisation (as assessed by personnel blinded to treatment allocation).

22.9.2021 Protocol version 9.2

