## Method:

*Design*: prospective, randomised, controlled, parallel group, open-label, assessor blinded feasibility trial.

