#### Sample study size:

We plan to randomise 36 patients in 1:1 ratio: This is a pilot trial, with primary outcome being feasibility and safety of faecal bacterial transplantation in the population of critically ill adults with C. dif. positivity and diarrhoea. However, with 36 randomised patients, the study will have sufficient power to determine non-inferiority against standard-of-care based on data available in FBT in patients with C. dif. In two trials in non-critically ill patients, the success of FBT was 69% (22 out of 32) or 56% (5 out of 9) as compared to 45% cured by oral metronidazole. Assuming that clinically significant difference between the two methods is 20% and the intervention will be as effective in ICU patients as it was in the non-critically ill group (curing 27 out of 41, ie. 66%), if there is a true difference in favour of the experimental treatment of 21%, then 36 patients are required to be 80% sure that the upper limit of a one-sided 95% confidence interval (or equivalently a 90% two-sided confidence interval) will exclude a difference in favour of the standard group of more than 20%. The expected duration of participation in the study is 6 months.

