## Informed consent procedure:

[figure not shown]
All patients with capacity will be asked to provide a prospective written informed consent (See Appendix 3). For patients without capacity, a deferred consent procedure will take a place. In this case, an independent clinician will review and sign that the patient is lacking capacity and he/she fulfils all criteria to be enrolled to the

Unique Protocol ID: 2021-002290-25 22.9.2021 Protocol version 9.2

study. The patient's next of kin will be informed about the study as soon as practical with the aid of information leaflet (Appendix 3). The patient will be asked to provide and sign informed consent as soon as he/she regains the capacity to do so. In case of consent refusal, patient's data will not be used in per-protocol analysis.

22.9.2021 Protocol version 9.2

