# Assessment of primary outcome:

An independent data analyst will retrospectively review the de-identified printouts of nursing notes from the two 12 hour shift day + night ending in the morning of day 7 and record the presence or absence of diarrhoea (defined as 3 or more stools per day or Bristol type 7 stool in the volume >300 ml/day if stool derivative device is inserted).

In case the patient is not on ICU, but remains at hospital, the research nurse will bring a special record form on day 6 and instruct both the patient and nursing staff to record during the next 24 hours the volume or frequency and consistency of stool using visual Bristol Scale and also to provide a sample of stool. In case the patient has been discharged, he/she will be contacted the day before over the phone by a research nurse and the next day the patient will be asked to bring the formulary and a stool sample to hospital of will be visited by a research staff at home.

Afterwards, as long as the patient remains on ICU, adverse events, antibiotic treatment, and stool volume/frequency are monitored daily.

Unique Protocol ID: 2021-002290-25 22.9.2021 Protocol version 9.2

In patients with faecal management device in place, follow up visits (identical to Day 4) are performed in 7 days interval up to day 28, and/or ICU discharge or FMD removal, whichever occurs earlier.

In patients who remain in ICU, but have had FMD removed, have the same follow up procedures, with the exception of stool sampling. Stool is collected and stored as close as practical to the day of the visit after the patient has had spontaneously defecated.

In patients who are not on ICU, but remain at hospital, will be visited by a research nurse at day 7, 14, 21 and 28 as long as they remain hospitalised. The visit will include monitoring of adverse event, notice on patient general status, the presence/absence of diarrhoea, antibiotic medication. Blood will be collected and frozen. Six month follow up is performed at follow up clinics and it includes history (incl. recent history of diarrhoea), physical exam and blood sampling. Patients willing to do so are requested to bring in a stool sample. Patients unwilling to show up will be interviewed over the phone.

	D0	D1	D2	D3	D4	D 5-6	D7	D14, 21, 28or D/C	6month follow up
ICF	х								
Review drug chart	Х								
Serum sample + freeze	х	x			х		x	x	х
Stool sample + freeze	х				х		х	(x)	х
Adverse events, Phys.exam, SOFA	х	х	х	х	х	х	х	х	
Blood culture		хх							

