# Statistical plan:

Safety parameters will be reported on intention-to-treat basis. Primary outcome will be compared by as unadjusted hazard ratio of not being cured (with 95% interval) in a per protocol analysis. The subset of patients with C. dif positivity will be analysed separately.

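### The Statistical plan specifies a hazard ratio for a yes/no outcome at day 7, so it cannot make the 20-point non-inferiority comparison that justifies 36 patients

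*Combined protocol and SAP*

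**What the plan says.** - **Primary end-point.** The outcome is the "Percentage of patients with treatment failure at day 7 after randomisation". Failure means "either failure to administer allocated treatment for any reason or the presence of diarrhoea on day 7 after randomisation".
- **Assessment of primary outcome.** An independent analyst reviews nursing notes for the two 12-hour shifts ending on the morning of day 7, to "record the presence or absence of diarrhoea". This is one yes/no reading per patient.
- **Sample study size.** The trial is described as a pilot, but the section adds that "the study will have sufficient power to determine non-inferiority against standard-of-care". The stated criterion is that the upper limit of a one-sided 95% interval "or equivalently a 90% two-sided confidence interval) will exclude a difference in favour of the standard group of more than 20" percent. The inputs are 45% cured on control, 66% cured on FBT and 80% power.
- **Statistical plan.** The primary comparison is an "unadjusted hazard ratio of not being cured (with 95% interval) in a per protocol analysis". The section states no margin, hypothesis, decision rule, event time or censoring rule, and does not define the per-protocol set.
- **Informed consent procedure.** For patients who refuse deferred consent, their "data will not be used in per-protocol analysis". This is the only exclusion from that set that the protocol states.
- **Method.** The design is an "open-label, assessor blinded feasibility trial".

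**The concern.** Three parts of the plan do not fit together.

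1. **Effect measure and endpoint.** A hazard ratio compares rates of a dated event over follow-up. The primary end-point is a status at one time, and nothing in the protocol defines cure as an event with a date.
2. **Analysis and sample size.** The margin is an absolute difference judged by a two-sided 90% interval. The planned result is a ratio with a 95% interval and nothing to judge it against.
3. **Denominator.** The endpoint counts undelivered treatment as failure. A per-protocol set in its usual sense drops exactly those patients, and the plan does not say which applies.

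As written, the effect measure, interval, analysis set and decision rule would be chosen once data exist, in a trial where treating clinicians know the allocation. The only stated justification for 36 patients would then correspond to no planned analysis.

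**Working it through.** **Inputs (Sample study size).** Cure is 45% on control and 66% on FBT (27/41), so failure is 55% and 34%. The margin is 20 points, one-sided alpha 0.05, power 80%, allocation 1:1.

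**Reproducing the plan's figure.** With the unpooled normal approximation on the risk difference:

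n per arm = (1.645 + 0.842)² × [0.45 × 0.55 + 0.66 × 0.34] / (0.21 + 0.20)² = 6.185 × 0.4719 / 0.1681 = 17.36

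This rounds up to 18 per arm, 36 in total, so the plan's number is right on the difference scale at one-sided 0.05. At one-sided 0.025, which matches a two-sided 95% interval, the same formula gives 46.

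**Can the margin be carried to a ratio?** Margin as a risk ratio = (control failure + 0.20) / control failure.

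| Control failure | Ratio at the margin |
|---|---|
| 34% (assumed) | 0.54/0.34 = 1.59 |
| 55% (implied by the protocol) | 0.75/0.55 = 1.36 |
| 75% (assumed) | 0.95/0.75 = 1.27 |

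Reading hazard ratio as a slip for risk ratio therefore does not recover the test. A hazard-ratio margin would also need proportional hazards: at 55% control failure it would be ln 0.75 / ln 0.55 = 0.48 for the hazard of cure.

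**Power on the difference scale.** Exact binomial enumeration, failure 34% against 55%, Miettinen-Nurminen interval, non-inferiority if the upper limit is below +20 points. Fewer than 18 analysed per arm is an assumption, because the protocol states no allowance for losses.

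| Analysed per arm | 90% interval | 95% interval |
|---|---|---|
| 18 | 79% | 69% |
| 17 | 77% | 66% |
| 16 | 75% | 63% |
| 15 | 74% | 61% |

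At 18 per arm with a 90% interval, Newcombe gives 80.9% and the normal approximation 81.3%. True one-sided error at the margin (75% against 55% failure) is 5.3% for Miettinen-Nurminen and 6.3% for Newcombe.

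**Undelivered treatment (assumed share u of the FBT arm).** If 34% is failure among treated patients only, FBT failure = 0.34 + 0.66u. For u = 5% this is 37.3%, and 90%-interval power at 18 per arm is 73%. For u = 10% it is 40.6% and power is 65%.

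**Effect of the denominator (assumed counts).** Control has 10/18 failures. In the FBT arm, 3 patients are not treated and 6 of the 15 treated have diarrhoea at day 7. Limits are from the 90% Miettinen-Nurminen interval.

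| Handling of the 3 untreated | FBT failure | Difference | Upper limit | Non-inferior? |
|---|---|---|---|---|
| Dropped | 6/15 | 40.0 − 55.6 = −15.6 points | +13.4 | Yes |
| Counted as failures | 9/18 | 50.0 − 55.6 = −5.6 points | +21.6 | No |

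**The case against.** The strongest reply is that this is a pilot. Hypothesis and aims speaks of feasibility, non-inferiority is no stated aim, and it enters Sample study size as a supplementary remark. That stands, and it is why deleting the claim is an acceptable repair. It does not rescue the analysis: the hazard ratio still does not estimate the day-7 endpoint, and the per-protocol set is still undefined.

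Stool is also recorded daily and in 12-hour intervals, so a time to resolution could be derived. That is true, but none is defined, and it would be a different outcome from the primary one. Equally, the day-7 data will allow a risk difference; the test is missing from the plan, not impossible with the data.

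Some limits on the figures are fair:

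- Whether power at full enrolment falls just below or just above 80% depends on the interval method.
- The preference for Miettinen-Nurminen rests on a modest difference in error at one pair of rates; the essential point is to name a method.
- The denominator example lies near the tipping point. With the same six diarrhoea failures and only one or two undelivered treatments counted as failures, the upper limits are +10.9 and +16.3, both within the margin. It shows that a reversal can happen, not that it is likely.
- The power loss from undelivered treatment may be partly double counting, since the protocol does not say how the cited trials handled such patients. It also loads non-delivery on the FBT arm only.
- That a per-protocol set would drop untreated patients is the usual meaning of the term, not something the protocol states.

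**Conclusion.** The concern holds and must be fixed. The planned hazard ratio does not match a binary day-7 endpoint, and the plan as written cannot make the comparison on which 36 patients were justified. The sample-size arithmetic itself is correct.

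The interval alone matters: using the Statistical plan's 95% level on the difference scale costs about 10 points of power (79% to 69%). These figures rest on the protocol's assumed rates and on all 18 patients per arm being analysed. The figures for losses, undelivered treatment and the denominator rest on assumed counts and illustrate sensitivity. The mismatch does not depend on them, and confidence in it is high.

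**What to change.** **Statistical plan**

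- Replace the hazard ratio with the difference in day-7 failure proportion (FBT minus control) and a two-sided 90% interval by one named method, preferably Miettinen-Nurminen.
- State that non-inferiority is concluded only if the upper limit is below 20 points.
- Analyse all randomised patients whose data may be used, with undelivered treatment counted as failure as the Primary end-point section requires. If a per-protocol set is kept, define it so that these patients stay in the denominator, and keep it consistent with Informed consent procedure.
- Make any time-to-resolution analysis a separate secondary outcome with its event defined.

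**Sample study size**

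- State that power of about 79% (Miettinen-Nurminen, 90% interval) needs 18 analysed per arm, and give the power for the losses and undelivered treatments expected.
- If the 95% interval is to decide, restate power as about 69%.

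**Alternative.** If non-inferiority is not intended, delete that claim and report the risk difference with its interval as an estimate.

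**Cost.** Wording only; 36 patients can stay. The price is a more modest power statement: just under 80% by the preferred method at full enrolment, and lower with any losses.

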## Direct access to source data/documents:

Whole FBT procedure must be properly recorded in accordance with the rules on medical records and the documentation must be store for 10 years. The patient documentation shall include the performance indication, performance record, informed consent to FBT and information obtained during subsequent visits. The documentation must be kept to allow for an additional assessment of possible early and late side effects of the method. Furthermore, it will be recorded from what 7 donors the extract was used for each individual patient.

Donor documentation includes the results of clinical and laboratory testing, a completed and signed questionnaire confirming the absence of exclusion criteria and informed consent to the use faeces for medical purposes. For each frozen faecal extract, the date of freezing and, where appropriate, the place of preservation must be indicated in addition to the donor identification.

The examiner and the medical facility will allow for clinical trial monitoring, audits, oversight of the ethics committee, inspection authorities inspection and access to source documents.

## **Quality control and quality assurance:**

To ensure compliance with Good Clinical Practices and all applicable regulatory requirement.

Acronym: FEBATIC

Unique Protocol ID: 2021-002290-25 22.9.2021 Protocol version 9.2

#### Ethics:

The final study protocol, including the final version of the Informed Consent Form, must be approved or given a favourable opinion in writing by in the Ethics Committee (EC) as appropriate. The Investigator is also responsible for informing the EC of any amendment to the protocol in accordance with local requirements. The investigator is also responsible for providing the EC with reports of any serious side effect of FBT therapy.

The study will be performed in accordance with the protocol, ethical principles that that have their origin in the Declaration of Helsinki WMA, and are consistent with Good Clinical Practice: Consolidated Guidelines and any applicable local regulation.

The Investigator(s) will ensure that subject (or the legal representative) is given full and adequate oral written information about the nature, purpose, possible risk and benefit of the study. Subject must also be notified that they are free to discontinue from the study any time. The subject (or the legal representative) should be given the opportunity to ask questions and allowed time to consider the information provided.

Voluntary written informed consent must be obtained before any study-related procedures are performed and the Investigator(s) must maintain the original, signed Informed Consent Form.

## Data handling and recordkeeping:

The team of investigators, together with independent safety advisors (prof. [name]. Dept. of Infectious Diseases, Na Bulovce Hospital, Prague and [name], REB Chair FNKV Univ Hospital) and representative of nursing staff independent on the study, are allowed to inspect subject charts, study source documents, drug accountability records and other records relative to study conduct. The Investigator must maintain all documentation to the study for a period of 5 years after the end of last study subject.

# **Publication Policy:**

Unique Protocol ID: 2021-002290-25 22.9.2021 Protocol version 9.2

We follow the authorship criteria established by the international Committee of medical Journal editors.

Minimum criteria for authorship credit based on: Substantial contributions to conception and design, acquisition of data or analysis and interpretation of data. Drafting the article or revising it critically for important intellectual content and final approval of version to be published. To be considered, all potential authors must fulfil all the minimum criteria for authorship credit.

 Dorsaz, S. et al. Changes in Microbiota Profiles After Prolonged Frozen Storage of Stool Suspensions. Front. Cell. Infect. Microbiol. 10, 1–8 (2020).
